**Physical Description of Study Drug(s)**

The Case 5815 tablet supplied for this study contains 60 mg of Apalutamide. It will be manufactured and provided under the responsibility of the sponsor. Refer to the Investigator's Brochure for a list of excipients.

**Packaging**

Apalutamide tablets (60-mg) will be packaged in 120-count, 160 cc high-density polyethylene (HDPE) bottles with child-resistant closures.

**Labeling**

Study drug labels will contain information to meet the applicable regulatory requirements.

**Preparation, Handling, and Storage**

The study drugs must be stored in a secure area and administered only to subjects enrolled in the clinical study in accordance with the conditions specified in this protocol. Refer to the pharmacy manual/study site investigational product manual for additional guidance on study drug preparation, handling, and storage.

[figure not shown]
**Drug Accountability**

The investigator is responsible for ensuring that all study drug received at the site is inventoried and accounted for throughout the study. The dispensing of study drug to the subject, and the return of study drug from the subject (if applicable), must be documented on the drug accountability form. Subjects must be instructed to return all original containers, whether empty or containing study drug. All study drug will be stored and disposed of according to the sponsor's instructions. Study-site personnel must not combine contents of the study drug containers. Study drug must be handled in strict accordance with the protocol and the container label, and must be stored at the study site in a limited-access area or in a locked cabinet under appropriate environmental conditions. Unused study drug and study drug returned by the subject, must be available for verification by the sponsor's study site monitor during on-site monitoring visits. The return to the sponsor of unused study drug, or used returned study drug for destruction, will be documented on the drug return form. When the study site is an authorized destruction unit and study drug supplies are destroyed on-site, this must also be documented on the drug return form.

Study drug should be dispensed under the supervision of the investigator or a qualified member of the study-site personnel, or by a hospital/clinic pharmacist. Study drug will be supplied only to subjects participating in the study. Returned study drug must not be dispensed again, even to the same subject. Study drug may not be relabeled or reassigned for use by other subjects. The investigator agrees neither to dispense the study drug from, nor store it at, any site other than the study sites agreed upon with the sponsor.

## 8.2 Leuprolide

Leuprolide acetate is a synthetic nonapeptide analog of naturally occurring gonadotropin releasing hormone (GnRH or LH-RH). The analog possesses greater potency than the natural hormone. The chemical name is 5-oxo-L-prolyl-L-histidyl-L-tryptophyl-L-seryl-L-tyrosyl-D-leucyl-L-leucyl-L-arginyl-N-ethyl-L-prolinamide acetate (salt) with the following structural formula

Leuprolide acts as an agonist at pituitary GnRH receptors. By interrupting the normal pulsatile stimulation of, and thus desensitizing, the GnRH receptors, it indirectly downregulates the secretion of gonadotropins luteinizing hormone (LH) and follicle-stimulating hormone (FSH), leading to hypogonadism and thus a dramatic reduction in estradiol and testosterone levels in both sexes.

LUPRON INJECTION is a sterile, aqueous solution intended for subcutaneous injection. It is available in a 2.8 mL multiple-dose vial containing leuprolide acetate (5 mg/mL), sodium chloride, USP (6.3 mg/mL) for tonicity adjustment, benzyl alcohol, NF as a preservative (9 mg/mL), and water for injection, USP. The pH may have been adjusted with sodium hydroxide, NF and/or acetic acid, NF.

As Lupron is a standard treatment for the management of prostate cancer. All patients will receive this agent according to institutional guidelines.

### **Pharmacodynamics and Pharmacokinetics**

Onset of action: Following transient increase, testosterone suppression occurs in ~2-4 weeks of continued therapy.

Distribution: Males: Vd: 27 L

Protein binding: 43% to 49%

Metabolism: Major metabolite, pentapeptide (M-1)

Bioavailability: SubQ: 94%

Excretion: Urine (<5% as parent and major metabolite)

## **9 Adverse Events and Potential Risks**

### **9.1 Management of Safety Data**

This Study has been designated as an interventional study. As such, all adverse events regardless of causality and special situations excluding those from subjects not exposed to a Janssen Medicinal Product and product quality complaints with or without an adverse event as described in this Exhibit will be reported from the time a subject has signed and dated an Informed Consent Form (ICF) until completion of the subject's last study-related procedure (which may include contact for follow-up safety). Serious adverse events will be reported for 30 days after the last dose of study drug.

For the purposes of this study, the Janssen medicinal product is Apalutamide.

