## 6.6 Duration of Follow up

All patients will be evaluated within 4-8 weeks after RP to rule out any potential AEs after discontinuation of the treatment. Any clinically significant abnormalities persisting at the end of the study will be followed by the investigator until resolution or until a clinically stable endpoint is reached. If patient has no AEs with regards to study agents this will be the last study related follow up.

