### 7.2 Apalutamide Dose Modifications in the Event of Toxicity

Dose interruptions and/or reductions for each patient will be permitted provided that study discontinuation criteria have not been met (please see Section 9.16 End of Treatment).

- Patients experiencing Grade 3 treatment-related adverse events will have study drug held until the severity of the toxicity decreases to Grade 1 or returns to baseline. If improvement occurs within 7 days, dosing may be restarted at the next level dose reduction. Exception to hold includes clinically insignificant lab abnormalities and hypertension, as deemed by the treating physician. Events that can be mitigated with optimal treatment within 2 days of the occurrence do not require a dose reduction; dose may resume at previous level.
- Any patient experiencing a drug related Grade 4 toxicity of any duration will be permanently discontinued.
- Patients experiencing treatment-related seizure of any grade or grade (G) 4 neurotoxicity will have study drug permanently discontinued.
- At any given dose level, if patients experience gastrointestinal (GI) discomfort due to the number of tablets, they will be allowed to switch to a BID regimen as needed.
- A maximum of one dose level reduction will be allowed.  
Any patient requiring Apalutamide treatment interruption longer than 7 days during the treatment period will meet the criteria for end of study treatment and study discontinuation.

**Table 1.** Apalutamide Dose Levels

Toxicity	Dose of Apalutamide (assuming 240 mg/day dosing)
Grade 1 or 2	No change
≥Grade 3 or higher	Hold until Grade 1 or baseline, resume at full dose
First Recurrence ≥Grade 3	Hold until Grade 1 or baseline, resume at 180 mg (3 tablets)
First occurrence of seizure of any grade or Grade 4 neurotoxicity	Discontinue
More than 7 days off treatment due to treatment related toxicity	Discontinue

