#### 9.2.5.2 Life-Threatening Conditions

The cause of death of a subject in a study within 30-days of the last dose of Apalutamide whether or not the event is expected or associated with the study drug, is considered a serious adverse event.

Disease progression should not be recorded as an adverse event or serious adverse event term; instead, signs and symptoms of clinical sequelae resulting from disease progression/lack of efficacy will be reported if they fulfill the serious adverse event definition.

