### 9.10 Reporting Procedures for Serious Adverse Events

For the purposes of safety reporting, all adverse events will be reported that occur after taking the first dose of Apalutamide through 30 days after the final dose of study drug. Adverse events, both serious and non-serious, and deaths that occur during this period will be recorded in the source documents. All SAEs should be monitored until they are resolved or are clearly determined to be due to a subject's stable or chronic condition or intercurrent illness (es). Related AEs will be followed until resolution to baseline or grade 1 or stabilization.

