### 9.16 End of Treatment

A patient may be discontinued from study treatment at any time if the patient, the Investigator and his (her) team, feels that it is not in the patient's best interest to continue on study. The following is a list of possible reasons for early discontinuation of study treatment:

- Disease progression
- Any episode of seizure
- Any other adverse event that cannot be adequately managed with dose modifications, including dose interruption for up to 7 days
- Protocol violation requiring discontinuation of study treatment
- Patient is not compliant with study procedures
- Lost to follow-up
- Patient withdrawal of consent
- Sponsor request for early termination of study

Patients will be followed for at least 28 +/-7 calendar days after the last dose of study drug. If a patient is withdrawn from treatment due to an adverse event, the patient will be followed until the adverse event has resolved or stabilized as per Section 7.6.

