### 14.1 Sample Size and Accrual

In a recent report by Chang et al the prevalence of the homozygous *HSD3B1*(1245C) genotype was 10% in 40 CRPC patients. The prevalence however is to some extent race-dependent.

The prevalence of the wild type and heterozygous genotypes were approximately 2:1, and therefore the homozygous variant genotype is “rate-limiting” for accrual. The target enrollment is 12 patients who have the homozygous *HSD3B1*(1245C) genotype, 15 patients who are heterozygous, and 30 wild-type patients. Because of the low prevalence of homozygous *HSD3B1* (1245C), enrollment in each cohort will proceed until its target is reached. A subject who either prematurely discontinues from the study before completing 28 days of the treatment, prior to surgery, or for whom we are unable to obtain a tissue sample from, may be replaced in order to achieve target enrollment in each cohort. All safety and efficacy data from all accrued patients independent of the availability of post-treatment tumor material will be collected and analyzed.

Overall, based on the prevalence of the homozygous variant genotype, we predict that we may need to screen up to 120 patients to reach our accrual objective. Due to logistical restrictions, an accrual goal of 80 male patients may be needed in order to capture all objectives for a sample size of 57 patients. Accrual is expected to be approximately 2 years in the three cohorts.

With 57 patients there will be statistical power >80% to detect a 4-fold trend in the primary endpoint, DHT concentrations in the resected prostate tissue, as well as similar trends in other androgens and molecular markers. The calculation is based on a 2-sided test with 5% type I error; a codominance model where there is a 4-fold difference in hormone concentration between the wild-type and homozygous variant genotypes and a concentration approximately mid-way between the two for the heterozygous genotype; and that variability in this concentration could be as much as 125% of the mean hormone tissue concentration for each genotype. Note that 125% of the mean is a conservative estimate of variability. If it turns out in fact to be lower – e.g. similar to the 75% seen in a recent study in which patients were treated with 6 months leuprolide prior to RP, there will be >95% power to detect a 4-fold range, >90% to detect a 3-fold range, and 75% to detect a 2-fold range.

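### SAE and death reporting runs 30 days from the last apalutamide dose and is not tied to prostatectomy, so men who stop early for toxicity get a shorter post-operative window than completers

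*Combined protocol and SAP*

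**What the plan says.** **Rules that count from the last dose**
- Section 9.1, second sentence: "Serious adverse events will be reported for 30 days after the last dose of study drug".
- Section 9.10: "all adverse events will be reported that occur after taking the first dose of Apalutamide through 30 days after the final dose of study drug". The same section extends this period to deaths.
- Section 9.2.5.2: "The cause of death of a subject in a study within 30-days of the last dose of Apalutamide" is treated as an SAE. The note in 9.2.5 sets the same limit for death from any cause.
- Section 9.16: "Patients will be followed for at least 28 +/-7 calendar days after the last dose of study drug". Section 9.16.2 places the safety follow-up 4 to 8 weeks after the last dose.

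**Rules that point to longer capture**
- Section 9.1, first sentence: all adverse events, whatever the cause, are reported until completion of the "last study-related procedure (which may include contact for follow-up safety").
- Section 6.6: "All patients will be evaluated within 4-8 weeks after RP".
- Section 9.2.5.1 makes a hospitalization during the study an SAE, apart from planned or social admissions, and sets no day limit.
- Sections 9.7 and 9.13 call for reporting of all SAEs without a closing date. Section 12.3 collects surgical safety data on clinic templates.
- Section 14.1: "All safety and efficacy data from all accrued patients independent of the availability of post-treatment tumor material will be collected and analyzed".

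**Early stopping**
- Section 7.2 ends apalutamide for a drug-related Grade 4 toxicity or a treatment-related seizure. It also says: "Any patient requiring Apalutamide treatment interruption longer than 7 days during the treatment period will meet the criteria for end of study treatment". That sentence goes on to make such a man a study discontinuation as well.

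**The concern.** Secondary objective 2.2.3 is the safety of leuprolide plus apalutamide given before prostatectomy, so the days after the operation are part of the question. A window anchored on the last dose gives completers almost a full post-operative month, because their last dose is taken the day before surgery. A man who stops early has already had the leuprolide injection and may still have his operation on the planned date, but his clock started earlier.

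The stopping rules in 7.2 select on toxicity. If the 30-day rule is followed, the men who tolerated treatment worst are observed for the fewest days after surgery. In a trial of 57 evaluable men and up to 80 accrued, one or two post-operative SAEs or deaths outside the window could change the safety summary. Early stops are foreseen: 5.1 and 14.1 provide for replacing men who do not complete 28 days, and 14.1 keeps every accrued man in the safety data.

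**Working it through.** The plan gives no figure to reproduce, so the check is calendar arithmetic with surgery as Day 0.

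**Inputs**
- Start of apalutamide, S: Day -31 to Day -25 (Day -28 ± 3; Protocol Summary and 6.2.1).
- Planned last dose: Day -1 (6.2.1).
- SAE and death window: 30 days after the last dose (9.1, 9.2.5, 9.2.5.2, 9.10).
- Shortest follow-up under 9.16: 28 - 7 = 21 days after the last dose.
- Post-operative visit: 4 to 8 weeks after surgery, about Day +28 to Day +56 (6.6).
- Assumptions: daily doses without gaps up to the stop, and surgery on its scheduled date.

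**Formulas**, for k doses taken
- Last dose = S + k - 1.
- Window closes = (S + k - 1) + 30 = S + k + 29.
- Shortest 9.16 follow-up ends = (S + k - 1) + 21 = S + k + 20.

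**Day on which the SAE and death window closes**

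| Doses taken | Start Day -31 | Start Day -28 | Start Day -25 |
|---|---|---|---|
| 1 | -1 | +2 | +5 |
| 7 | +5 | +8 | +11 |
| 14 | +12 | +15 | +18 |
| 21 | +19 | +22 | +25 |
| Full course (last dose Day -1) | +29 | +29 | +29 |

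For a Day -28 start, the post-operative coverage relative to a completer is 2/29 = 7%, 8/29 = 28%, 15/29 = 52% and 22/29 = 76% after 1, 7, 14 and 21 doses.

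**When does the window close before surgery?** This needs S + k + 29 < 0. Within the permitted start days, only S = -31 with k = 1 meets it (-31 + 1 + 29 = -1). Otherwise the operation must be delayed. From a Day -28 start, the delay would have to be at least 3, 9, 16 or 23 days after 1, 7, 14 or 21 doses.

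**When does it close soon after surgery?** It closes by Day +7 for stops within the first 9, 6 or 3 doses (start Day -31, -28, -25), and by Day +14 for stops within the first 16, 13 or 10 doses.

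**Shortest 9.16 follow-up**, Day -28 start: one dose gives -28 + 1 + 20 = Day -7, and seven doses give -28 + 7 + 20 = Day -1. Both fall before surgery. This is a floor, since 9.16 says at least.

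**Do the other sections close the gap?** The first sentence of 9.1 and the visit in 6.6 would cover an operated man to about Day +28 to Day +56, whatever his last dose. But the next sentence of 9.1 sets a specific limit for SAEs, and 9.10 applies 30 days to all adverse events and deaths. A visit under 6.6 may find an event without bringing it inside the reporting window. For men off drug more than 7 days, 7.2 ends the study as well as the treatment, so it is unclear whether 6.6, or the during-the-study wording of 9.2.5.1, still applies to them. Section 9.16 follows the event that caused withdrawal, not new post-operative events, and refers to a section 7.6 that the protocol does not contain. None of these passages extends the explicit death window.

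**The case against.** The strongest reply is that capture does not stop at 30 days. The first sentence of 9.1, together with 6.6, 9.2.5.1, 9.7, 9.13, 12.3 and 14.1, offers routes with no last-dose limit, and no passage says that later events are left out of the safety analysis. This stands. A reader might infer that post-operative SAEs and deaths in early stoppers will simply not be counted. The documents do not support that: they give conflicting end dates and do not say which governs.

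A reader might also infer that the window generally closes before the operation. With surgery on schedule it does so only for a single dose taken on Day -31. A stop after 21 doses still leaves 19 to 25 post-operative days.

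It can further be said that a drug-anchored window is a legitimate choice, since every man has the same 30 days after exposure and 9.2.1 deliberately keeps surgical events apart from treatment-related ones. That is fair for drug safety alone. It is less convincing for an objective that concerns treatment given as preparation for surgery.

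Finally, the trial is single-arm, 14.2 plans no comparison of early stoppers with completers, and 1.2 reports no treatment-related SAEs in the Phase 2 part of the earlier apalutamide study, so few men may be affected. This limits the likely impact. It does not remove the conflict.

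**Conclusion.** The point holds as a conditional shortfall resting on an internal conflict. Every explicit SAE and death window runs from the last apalutamide dose. If those windows govern, men who stop early for toxicity and are operated on as scheduled have between 2 and 22 post-operative days of SAE and death reporting (Day -28 start, 1 to 21 doses), against 29 for completers. Bringing all sections to 30 days after the last dose would remove the inconsistency but keep the shortfall.

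The size rests on surgery taking place on its scheduled date; the documents do not say what happens to that date after an early stop. The number of men affected, and hence the effect on the safety results, cannot be computed because no early-stop rate is given. The change is worth making because it is cheap and bears on objective 2.2.3. The documents do not show that events will be lost.

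**What to change.** 1. In 9.1 (second sentence), the 9.2.5 note, 9.2.5.2 and 9.10, end SAE and death reporting, for every treated man who has surgery, at the later of 30 days after the last apalutamide dose and 30 days after prostatectomy. Since the last dose is at the latest Day -1, this means Day +30 for all operated men. If the sponsor prefers, the 6.6 visit can replace the second limit, but its date varies between men.
2. Reconcile these sections with the first sentence of 9.1 and with 9.2.5.1, and align 9.16 and 9.16.2, including the reference to section 7.6.
3. State that the 6.6 visit applies to men discontinued under 7.2.
4. Report post-operative SAEs and deaths over the same period after surgery for all operated men, completers and early stoppers alike, with surgical adverse events identified separately to respect 9.2.1.

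The cost is protocol wording and a few more SAE reports, some of them due to surgery itself. No new visit is needed, because 6.6 already plans one. A visit at exactly 4 weeks (Day +28) falls two days short of Day +30, which a safety contact of the kind 9.1 mentions would cover. No dose or treatment rule changes.

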### **9.2 Definitions**

#### **9.2.1 Adverse Event (AE)**

An adverse event is any untoward medical occurrence in a clinical study subject administered a medicinal (investigational or non-investigational) product. An adverse event does not necessarily have a causal relationship with the treatment. An adverse event can therefore be any unfavorable and unintended sign (including an abnormal finding), symptom, or disease temporally associated with the use of a medicinal (investigational or non-investigational) product, whether or not related to that medicinal (investigational or non-investigational) product. (Definition per International Conference on Harmonisation [ICH])

This includes any occurrence that is new in onset or aggravated in severity or frequency from the baseline condition, or abnormal results of diagnostic procedures, including laboratory test abnormalities.

Surgical AEs such as urinary incontinence, erectile dysfunction and wound complications will be assessed per institutional guidelines. These will not be captured as part of treatment related AEs.

#### **9.2.2 Adverse Events of Special Interest**

Adverse events of special interest are events that the COMPANY is actively monitoring as a result of a previously identified signal (even if non-serious).

There are no adverse events of special interest identified for apalutamide.

### 9.2.3 Identified Individual Case Safety Report (ICSR)

A valid ICSR must contain the four minimum criteria required to meet regulatory reporting requirements.

- An identifiable subject (but not disclosing personal information such as the subject's name, initials or address)
- An identifiable reporter (investigational site)
- A Janssen medicinal product
- An adverse event, outcome, or certain special situations

The minimum information required is:

- Suspected Janssen medicinal product (doses, indication)
- Date of therapy (start and end date, if available)
- Batch or lot number, if available
- Subject details (subject ID and country)
- Gender
- Age at AE onset
- Reporter ID
- Adverse event detail (AE verbatim in English), onset date, relatedness, causality, action taken, outcome, (if available)
- Janssen protocol ID

### 9.2.4 Product Quality Complaint (PQC)

A product quality complaint is defined as any suspicion of a product defect related to a potential quality issue during manufacturing, packaging, release testing, stability monitoring, dose preparation, storage or distribution of the product, or delivery system. Not all PQCs involve a subject. Lot and batch numbers are of high significance and need to be collected whenever available.

Examples of PQC include but not limited to:

- Functional Problem: e.g., altered delivery rate in a controlled release product
- Physical Defect: e.g. abnormal odor, broken or crushed tablets/tablets
- Suspected Contamination
- Suspected Counterfeit

